Eligibility will be determined by a University of Pittsburgh Post-Cardiac Arrest Service (PCAS) physician, all of whom are routinely consulted in the care of this patient population and will serve as co-investigators on the study. Inclusion and exclusion criteria will be based on clinical characteristics (see attached Screening questionnaire). Due to the urgent need for intervention in this population, we will enroll subjects under an exception from informed consent (EFIC). Once eligibility is determined, patients will be randomized using block randomization to receive iNO or placebo. Randomization will be stratified in blocks of 8 by center. The randomization list will be created prior to the beginning of the study by the Respiratory Therapy (RT) directors ([name], PUH, and [name], MER) and confirmed by a representative of Mallinckrodt. These 3 individuals who will not be involved in any portion of the conduct or analysis of the study will retain these lists and update them as additional subjects are enrolled using new canisters of study drug. This list will set an order in which canisters of iNO study drug, coded by bar code, will be administered at each site. Treatment assignment will be made known to the study team after enrollment is confirmed by means of a sealed opaque envelope which contains the cylinder barcode for the subject as well as the subject ID. These envelopes will be with other research materials at each study site. iNO canisters will be stored in PUH Rm A-125 and Mercy (ED compressed gas storage). Prior to each enrollment the next canister to be used at a site will be loaded onto an iNOVent delivery device and the gas calibrated permitting rapid deployment to the next subject enrolled at that site. Check lists will be maintained as each site documenting calibration and each use on a study subject. The gas canister bar code will be recorded in our

database with the subject ID permitting subsequent unblinding of treatment assignment. Canisters will be used for 4 subjects prior to return to the company and replacement with a new (full) canister of study drug.

A clinical respiratory therapist (RT) will administer iNO at 20 ppm for 12h, with a 1h wean consisting of 10 min at 10 ppm, 10 min at 5 ppm, 10 min at 4 ppm, 10 min at 3 ppm, 10 min at 2 ppm, and 10 min at 1 ppm before subject is taken off of study drug. Study drug will generally be connected in the emergency room or ICU.

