The following data elements will be collected during the course of the study at the times indicated. Data elements marked with an asterisk indicate variables or outcomes essential for conduct of the study and analysis of efficacy and/or safety. These data elements should be obtained in all subjects with no missing data expected. In addition to these data elements, we are collecting a large amount of secondary data intended for use in mechanistic studies and hypothesis generation. In many cases, these data elements WILL NOT be able to be collected in all subjects. Such missing data will be handled as designated within an a priori statistical analysis plan but the presence of missing data will in no way impede our ability to meet the objectives of this phase 2 RCT.

BASELINE DATA

- *Date of OHCA
- *Time of OHCA (If not available we will use Time of ROSC after subtracting estimated no flow and CPR time based on transfer records/physician report)
- Witnessed
- Bystander CPR
- EMS Call Date
- EMS Call Time
- EMS Arrival Date
- EMS Arrival Time
- No flow time
- CPR (low flow) time
- Presenting rhythm
- *Date and Time of ROSC (If not available we will use ED admission date/time from referring hospital record. If unavailable, stat medevac call date/time minus 30 mins. If unavailable, time of arrival minus 15 min)
- PCAS ID
- *Last name
- *First name
- *Date of Birth
- *Medical record number
- Marital status
- Race/Ethnicity
- *Male Sex
- *Height
- *Weight
- Post-resuscitation chest pain

- Charlson Comorbidity
- Age Adjusted for Charlson Comorbidity Index (CCI)
- *New York Heart Association (NYHA) class pre-OHCA (if no surrogate is present and no medical records are found on the subject this will be assumed to be NYHA class I)
- Barthel ADL pre-OHCA
- Education level
- Private insurance
- Medicare
- Medicaid
- Employed
- Active smoker
- Smoker >20 pack-years
- Prior stroke
- Prior Coronary artery bypass grafting (CABG)
- Noninsulin-dependent diabetes mellitus (NIDDM2) type 2
- Insulin-dependent diabetes mellitus (IDDM2) type 2
- Diabetes mellitus (DM1) type 1
- Prior myocardial infarction (MI)
- Congestive Heart Failure (CHF)
- Chronic Obstructive Pulmonary Disease (COPD)
- Prior cardiac arrest
- Dementia
- Hyperlipidemia
- Hypertension
- Prior coronary stent
- Obstructive sleep apnea
- Pulmonary hypertension
- *Location pre-OHCA

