2.3 STUDY DRUG

2.3.1. Study Drug Preparation and Dispensing

iNO used in this study will be sourced and formulated by INO Therapeutics, part of Mallinckrodt Hospital Products IP Limited. Cross reference authorization has been granted to us by Mallinckrodt for information on the study drug, known as INOmax under New Drug Application (NDA) 20-845. Placebo gas wherein nitrogen (the carrier vehicle gas) is substituted for iNO will also come from Mallinckrodt.

Mallinckrodt will deliver gas cylinders to the Respiratory Therapy (RT) Department at UPMC PUH or MER. Each cylinder will have a bar code which corresponds to its contents (iNO or placebo). Randomization will be done in advance in blocks of 8 at each site by the RT directors using the website <http://www.graphpad.com/quickcalcs/randomize1.cfm>. The random order list generated will list the order in which subjects coming in to each site are assigned to cylinders of study drug. In each group of 8, 4 subjects will be assigned to one placebo cylinder and 4 subjects will be assigned to one iNO cylinder. RT will dispense study drug upon patient enrollment and the blinded research assistant (RA) will transport the cylinder/iNOvent, making note of its barcode to permit subsequent treatment assignment, to the patient's bedside for connection to the ventilator by RT. All patients will be on mechanical ventilation via an endotracheal tube (ETT). iNO is a commonly used drug within UPMC and existing protocols for its use will be followed in connecting the drug to the ventilator circuit.

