2.5.2 Study Conduct Analysis

Continuous data will be summarized and compared using t-tests or a non-parametric equivalent should the normality assumption appear tenuous. Generalized linear mixed models, which account for non-independence of repeated assessments and endpoint structure, will be used to compare between iNO and placebo groups at multiple times. Analysis of the composite endpoint will be ascertained using an unadjusted two sample test of proportions with a type II error rate of 5%. In the event of imbalance of potential confounders after randomization an adjusted analysis will be performed using logistic regression with those unbalanced variables and treatment as the main effect of interest. Other secondary dichotomous outcomes will be summarized and compared by chi squared tests and appropriate exact methods should sample sizes be small. Time to event endpoints will be summarized by Kaplan Meir curves and compared using log rank tests. All tests will be two tailed with unadjusted $p < 0.05$ considered significant and performed using SAS 9.4.

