2.5.5 Handling Missing Data

Since our primary endpoint is ascertained at hospital discharge we expect no missing data though all analyses will be performed assuming a missing at random mechanism. No data imputation will be performed though standard sensitivity analyses, using standard missing data techniques may be used.

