3.2 INCLUSION CRITERIA

Inclusion criteria do not change any subgroups.

Intubated and comatose adult (>18 yo)

Out-of-hospital cardiac arrest (OHCA)

Cardiac arrest within an emergency department or outpatient medical center will be included.

OHCA includes EMS witnessed cardiac arrest.

ROSC within 40 min of CPR initiation

FOUR Brainstem score ≥ 2

Patient must have pupil OR corneal reflex before enrollment

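### The composite's primary test is valid but uses no baseline covariates, and its only adjusted model picks covariates by chance imbalance, with no candidate list or threshold

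*Combined protocol and SAP*

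**What the plan says.** All references are to the combined protocol and SAP.

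- **Primary test (Section 2.5.2):** "Analysis of the composite endpoint will be ascertained using an unadjusted two sample test of proportions". Section 2.5.1 sizes the trial on the same kind of test.
- **Adjusted model (Section 2.5.2):** "In the event of imbalance of potential confounders after randomization an adjusted analysis will be performed using logistic regression with those unbalanced variables". Neither this section nor any other names the candidates, sets a threshold for imbalance, or says which result governs if the two differ. Section 2.5.3 mentions adjusted regression only for the physiologic surrogate.
- **Randomisation:** Section 2.2 states "Randomization will be stratified in blocks of 8 by center". Section 2.3.1 adds "In each group of 8, 4 subjects will be assigned to one placebo cylinder", with the other four on one active cylinder. No analysis of the composite includes centre.
- **Baseline data (Section 2.2):** date of birth carries the asterisk that marks items expected to be complete. Presenting rhythm and low-flow time do not. Of the data without an asterisk the section says: "In many cases, these data elements WILL NOT be able to be collected in all subjects".
- **Missing data (Section 2.5.5):** "No data imputation will be performed".

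**The concern.** In a randomised trial, adjustment gains precision from covariates that predict the outcome. A chance difference between arms is a poor reason to select one: a strong predictor that happens to balance is left out, and a weak one that happens to differ goes in. The rule also cannot be applied until the data are grouped by arm, and the pool and threshold are then left to the analyst.

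Precision is at stake, together with a supporting analysis that nobody can specify in advance. Section 2.5.1 claims just over 80% power, so there is little slack. Section 2.5.3 says that the primary outcome is meant to establish efficacy, so the analyses around it should be fixed beforehand.

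**Working it through.** **Inputs from the documents.** Control rate 80-85%, a 23-point reduction, 60 evaluable per arm, and 65 enrolled per arm with 5% dropout (Section 2.5.1). Two-sided 0.05 (Section 2.5.2). 1:1 allocation in blocks of 8 within centre (Sections 2.1, 2.2 and 2.3.1).

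**Assumptions, not in the documents.** Centre split 84/40 and centre log-odds 0.3. Three equally weighted covariates (two normal, one binary at 40%) with combined log-odds SD 0, 0.4, 0.8 or 1.2. These give a control-arm AUC of 0.53, 0.62, 0.71 and 0.78; the 0.53 comes from centre alone.

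**1. The plan's own figure.** Power = Φ{[δ − 1.96·√(2p̄(1−p̄)/n)] / √[(p1(1−p1)+p2(1−p2))/n]}. For 80% versus 57% with n = 60, p̄ = 0.685, the null SE is 0.0848 and the alternative SE is 0.0822. Then (0.23 − 0.1662)/0.0822 = 0.776, and power is 78.1%. Control rates of 82.5% and 85% give 80.1% and 82.3%. The stated figure reproduces to within rounding. At 62 per arm (65 × 0.95 = 61.75) the three values are 79.5%, 81.4% and 83.5%.

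**2. How often the trigger fires.** With k independent candidates and an assumed p<0.05, the chance is 1 − 0.95^k. For k = 4 this is 1 − 0.8145 = 18.5%; simulation gave 18.7-19.2%.

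**3. What the trigger does to power.** Simulation at 62 per arm, 80% versus 57%, 6,000 trials per setting, four candidates of which three are prognostic. Changes here and below come from unrounded figures, so they can differ by 0.1 from the rounded powers.

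| Rule | AUC 0.53 | 0.62 | 0.71 | 0.78 |
|---|---|---|---|---|
| Unadjusted | 80.7% | 79.4% | 80.8% | 80.2% |
| Trigger at p<0.05 | 80.3% | 79.4% | 81.0% | 80.9% |
| Trigger at standardised difference >0.1 | 79.8% | 79.0% | 82.4% | 84.1% |

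At p<0.05 the change is -0.5 to +0.7 points. The loose trigger fires in 96-97% of trials and changes power by -0.9, -0.5, +1.7 and +3.9 points, because it then nearly always adjusts for something. The benefit therefore depends on a threshold that the plan does not state. Null rejection across all trigger settings was 4.0-4.9%.

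**4. A fixed list that is always used.** Treatment, centre and the three covariates, with the p-value from re-randomising within centre and blocks of 8. 62 per arm, 80% versus 57%, 10,000 trials per setting, 999 re-randomisations, Monte Carlo SE 0.4 points on power.

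| | AUC 0.53 | 0.62 | 0.71 | 0.78 |
|---|---|---|---|---|
| Unadjusted | 80.1% | 80.1% | 79.3% | 79.3% |
| Fixed list | 78.6% | 80.2% | 82.3% | 86.1% |
| Change | -1.5 | +0.1 | +3.0 | +6.8 |
| Change with 15% missing rhythm and 15% missing low-flow time | -2.3 | -0.7 | +1.5 | +5.2 |

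A separate, smaller simulation (62 per arm, residual permutation test, 1,500 trials per setting, SE about 1 point) gave -1.4, 0.0, +2.3 and +7.0 at 80% versus 57%. At 85% versus 62% it gave -1.7, -0.1, +2.1 and +3.3.

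**5. Level of the tests (null 82.5% in both arms).** Unadjusted 4.7-5.1%. Permutation 4.5-5.1%, or 4.6-5.3% with missing covariates. The uncorrected adjusted test ran at 5.7-6.6%, or 6.8-7.2% with missing covariates; a plain logistic likelihood-ratio test at 65 per arm (null 80%) ran at 5.5-6.0%. So about 5.5-7% if left uncorrected.

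**6. How often results split across 0.05 (80% versus 57%).** Triggered versus unadjusted (four candidates, p<0.05): 1-3%. Fixed list versus unadjusted: 4%, 5%, 9% and 11% in AUC order.

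**The case against.** The strongest reply is that nothing is broken. The primary test holds its level, Sections 2.5.1 and 2.5.2 name it without condition, and a model that may never be fitted cannot sensibly be primary. The trigger is limited to potential confounders, which ordinarily means variables related to outcome. The benefit of adjustment is also assumed. Section 3.2 restricts entry ("ROSC within 40 min of CPR initiation", plus brainstem function), and Section 3.3 removes patients at both prognostic extremes, so prediction within the trial may be weak. Most of this stands, and it rules out several stronger readings that a reader might infer.

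- *The trigger inflates type I error.* It ran at 4.0-4.9%. Even claiming success when either result is significant gave only about 5.6-5.9% (eight candidates, p<0.10, 65 per arm), and the plan does not provide for that.
- *The plan leaves its primary result open.* The text points to the unadjusted test; only an explicit sentence is missing.
- *The trigger costs several points of power.* Losses of 3.0 to 3.8 points appear only with 38 candidates, 35 of them noise, a pool that the plan does not state.
- *No baseline information is used at all.* Section 2.4 builds pre-arrest heart failure class and residence into the endpoint. What is absent is baseline covariates in the test.
- *The adjusted analysis ought to be primary.* The gain is nil or negative at the two weaker assumed strengths and smaller at the 85% control rate. It also brings a confidence interval that disagrees with the permutation p-value in 1.8-2.8% of trials.

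The reply does not rescue the selection rule. Even if every candidate is prognostic, the rule uses only those that happen to differ, and neither pool nor threshold is written down.

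**Conclusion.** The concern holds as a choice of method, at the level of something to consider. The unadjusted test is valid and is best read as primary. The supporting adjusted model selects on the wrong criterion and is not defined. Under the most natural concrete version (four candidates, p<0.05) it is fitted in about one trial in five and moves power by less than a point either way.

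If the team chose to make a fixed-list analysis primary, power would change by about -1.5 to +7 points at 80% versus 57% (about -2.3 to +5.2 with 15% missing covariates), and by about -1.7 to +3.3 at 85% versus 62%. These ranges rest on an assumed control-arm AUC of 0.53 to 0.78, an assumed centre split and effect, and independent covariates. The documents give no prognostic strength, so they do not show that a gain would be realised. They support replacing the trigger with a fixed list; they do not settle which analysis should be primary.

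**What to change.** Before unblinding, amend Section 2.5.2 as follows.

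1. Delete the imbalance trigger. Specify one adjusted analysis of the composite that is always run, with treatment, centre, age, shockable versus non-shockable rhythm, and low-flow time. All are already collected.
2. Add a missing-category rule for rhythm and low-flow time, based on baseline data only, and cross-reference it to the no-imputation statement in Section 2.5.5.
3. Report the standardised risk difference with a small-sample-corrected 95% CI. Take the p-value from a method that respects the centre-stratified blocks, such as re-randomisation within centre and blocks of 8, and say that this p-value prevails if it and the interval disagree.
4. State which result governs. By default the unadjusted test stays primary, as Sections 2.5.1 and 2.5.2 imply, and the fixed-list model is supporting. The sentence matters more once the model is always run, because the two would then split across 0.05 in 4-11% of simulated trials. Making the adjusted analysis primary is an option for the team.

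The cost is a wording change through the route in Section 4 (prospective IRB approval, and an IND amendment if the change is judged to affect scientific quality significantly), and slightly more analysis work. No new data are needed. Up to about 2 points of power are at risk only if the adjusted analysis is made primary and the covariates do not predict the composite.

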2.5.3 Efficacy Analysis

Our primary outcome is intended to prove efficacy. Improvement in any of the secondary clinical outcomes being assessed would be considered preliminary evidence of efficacy requiring a subsequent larger trial for proof. Since iNO's effects on pulmonary vasodilation are best known, we will use this as our primary physiologic surrogate measure of iNO efficacy and will be compared using unadjusted two-sample tests or adjusted regression based methods.

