Study Aims:	
 1. Determine whether iNO (compared to placebo) provides clinical benefit when used within 4h of ROSC after OHCA. 2. Determine which mechanistic pathways are activated through use of iNO therapy and whether any of these are associated with outcome. 3. Determine whether iNO at 20 ppm provides a physiologic effect as determined by a significant reduction in tricuspid regurgitant velocity compared to placebo. 4. Determine whether RH measured by LSCI predicts subjects who will have a physiologic and/or clinical response to iNO.

	
5. Determine whether iNO reduces oxidant stress and mitochondrial injury after OHCA compared to placebo.
 
6. Measure plasma nitrite and S-nitrosothiol levels, as a surrogate of total plasma bioavailable NO, in all subjects.

Study Design:	Phase II double blind (participants and investigator) placebo controlled randomized (1:1) clinical trial of iNO 20 ppm administered over 12 hrs beginning as soon as possible but within 4 hrs of ROSC after OHCA.
Planned Sample Size:	130 subjects
Duration of Treatment:	12h
Major Inclusion Criteria:	
Intubated and comatose adult (>18 yo)
 
Out-of-hospital cardiac arrest (OHCA)
 
Cardiac arrest within an emergency department or outpatient medical center will be included.
 
OHCA includes EMS witnessed cardiac arrest
 
ROSC within 40 min of CPR initiation
 
FOUR Brainstem score ≥ 2
 
Patient must have pupil OR corneal reflex before enrollment

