- *Best estimate of CPC pre-OHCA (if no surrogate is present and no medical records are found on the subject this will be assumed to be CPC 1)
- *Best estimate of mRS pre-OHCA ((if no surrogate is present and no medical records are found on the subject this will be assumed to be mRS 0)
- Rib fracture after ROSC
- Sternal fracture
- Witnessed aspiration
- Infection present at baseline
- Infection type
- Sputum color
- Vent mode
- Set Tidal Volume (V_t) or Inspiratory Pressure (P_{insp})
- Positive end expiratory pressure (PEEP)
- Fraction of inspired oxygen (FiO₂) expressed as % oxygen
- Peak Pressure (PIP)
- Plateau Pressure (P_{plat})
- Chest X-Ray reading possibly consistent with pneumonia
- Positive airway culture

Toxicology report

Cause of arrest

History of drug/alcohol use

Current drug/alcohol use

- ECHO RESEARCH ONLY To be performed by PCAS physician or research assistant trained by [name], who is a cardiologist and Associate Professor of Medicine at the University of Pittsburgh.
 - o Tricuspid valve regurgitant velocity
 - o Aortic valve velocity (CO estimate)
 - o Pulmonary valve velocity
 - o Tricuspid annular plane systolic excursion (TAPSE)
 - o LVEF
- *LSCI RESEARCH ONLY To be performed by a research assistant trained by the PI. A complete description is available in section CS10.1.
 - o Baseline blood flow and RH after 1 min vasoocclusion [resolution 1 image/s; 10 image/s averaging]
 - o Baseline blood flow and RH after 5 min vasoocclusion [begin 5 min after last test]*
 - *Baseline labs (troponin, arterial blood gas, lactate, plasma nitrite level,)
 - Additional plasma labs (neuron specific enolase, platelet mitochondria, ascorbate, cardiolipin, SNO, cGMP, plasma banking)
 - Urine labs (renal failure and nitrated fatty acid measurements)
 - Blood for genomics (retained unless informed consent declined)
 - *Baseline vital signs VS (temperature, heart rate [HR], mean arterial blood pressure [MAP], arterial oxygen saturation [SpO2])

STUDY DRUG (0-12 h) DATA

(Refer to Chart below)

- *Every 3 hour vital signs VS (temperature, HR, MAP, SpO2)
- Hourly monitoring of VS, SAEs, vent settings
- Pulmonary Arterial Pressures (systolic, diastolic, mean) – often not available
- Central Venous Pressure – often not available
- SvO2 – often not available
- *Plasma labs at 6 and/or* 12 h (troponin, arterial blood gas, lactate, methemoglobin, plasma nitrite level)

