2.4 STUDY ENDPOINTS

Primary

Composite of in-hospital death, unfavorable discharge location, NYHA class III/IV heart failure at the time of discharge*

*In the setting of pre-existing heart failure or prior residence in an unfavorable location there must be at least a 1 class decrement (eg NYHA III -> IV)

Secondary

Functional

- Survival to hospital discharge, 30 and 90 days after initial OHCA
- Favorable cerebral performance category (CPC) defined as 1 or 2 at discharge, 30 and 90 days after initial OHCA
- Favorable modified Rankin score (mRS) defined as 0-3 at discharge, 30 and 90 days after initial OHCA
- Favorable discharge destination or location of residence (30 and 90 days after OHCA) defined as home or acute inpatient rehabilitation
- CPC-E at hospital discharge, 30 and 90 days after initial OHCA
- Barthel Index of Independence in Activities of Daily Living (ADL) at discharge, 30 and 90 days after OHCA

Neurologic

- Estimated likelihood of good neurologic outcome (0-100%) assessed by an experienced (>3y) member of the PCAS team blinded to treatment assignment on day 3-5 post-ROSC.
- Development of malignant EEG during hospitalization

- Time (in hours) to awakening from ROSC; defined as following commands (all values > 96h assigned 100)
- FOUR Motor + Brainstem scores on days 1-3 (requires 30 min off sedation; exclude endpoint if not medically permitted to pause sedation or paralysis)
- Presence or absence of upper and lower extremity somatosensory evoked potential N20 on comatose patients obtained any time after post-arrest day 1.
- Absolute value 24h after ROSC and change in value (24h vs 0h) of neuron specific enolase (NSE)
- EEG burst suppression ratio and change in suppression ratio
- EEG presence of dominant continuous background and reactivity to photic or tactile stimulation.

Cardiovascular

- Heart rate and mean arterial pressure (preferably off the arterial line) at 0-12 (hourly), 24h of study drug
- Persistent need for vasopressors in the first 24h after ROSC; defined as any use of norepinephrine, epinephrine, phenylephrine, dopamine or vasopressin for ≥ 3 h after study drug is initiated
- Persistent need of inotropes in the first 24h after ROSC; defined as any use of epinephrine, dobutamine, milrinone or isoproterenol for ≥ 3 h after study drug is initiated.
- ECHO measures (absolute values at end of therapy (12h) and change in 12h vs 0h):
 - tricuspid valve regurgitant velocity (TRV)

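### Tricuspid regurgitant velocity is the named test of iNO's physiologic effect, but it is off the must-collect list and the plan cannot tell an absent jet from an echo not done

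*Combined protocol and SAP*

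**What the plan says.** - **Role of TRV.** Aim 3 in the Protocol Synopsis asks whether 20 ppm has a "physiologic effect as determined by a significant reduction in tricuspid regurgitant velocity compared to placebo". Section 2.5.3 says of pulmonary vasodilation that "we will use this as our primary physiologic surrogate measure of iNO efficacy", to be compared by unadjusted two-sample tests or adjusted regression. Section 2.4 lists TRV first under "ECHO measures (absolute values at end of therapy (12h) and change in 12h vs 0h").
- **Collection status.** Section 2.2 explains the marking: "Data elements marked with an asterisk indicate variables or outcomes essential for conduct of the study and analysis of efficacy and/or safety". Starred items are expected to be complete. Of the remaining items it says: "In many cases, these data elements WILL NOT be able to be collected in all subjects". The baseline entry, "ECHO RESEARCH ONLY To be performed by PCAS physician or research assistant", has no asterisk, and neither does the 11-12 h echo. Laser speckle imaging (LSCI) has one at both times. Pulmonary artery catheter pressures are listed as often unavailable, so TRV is the practical measure of this surrogate.
- **Missing data.** Section 2.2 promises that missing mechanistic data will be handled in a pre-written analysis plan. The only such text in the combined document is section 2.5.5, which assumes missing at random for every analysis and adds: "No data imputation will be performed though standard sensitivity analyses, using standard missing data techniques may be used".
- **Silent on:** how an unmeasurable jet is recorded, how much missing TRV is expected, and the standard deviation of TRV.

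**The concern.** Two things do not fit together. The quantity chosen to show that the drug acts on the pulmonary circulation is grouped with data that may go uncollected. And the reason it is missing may be tied to its value: TRV is the speed of a regurgitant jet, so no measurable jet means no number. If subjects with lower pulmonary pressure more often lack a measurable jet, an effective drug would remove some of its own responders from the comparison, and an available-case analysis would shrink the difference.

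Aim 3 is at stake. A false finding of no physiologic effect would colour the reading of a neutral primary result. It would also feed into Aim 4, which judges LSCI partly against physiologic response. As the data are to be recorded, an absent jet and an echo that was not done look the same, so the assumption could not be examined afterwards.

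**Working it through.** **The plan's own figure.** Section 2.5.1 gives no power for TRV. It says only that the trial is overpowered for a fall in pulmonary artery pressure of 20-25 mm Hg, with no standard deviation (SD). For 80% power, two-sided 5%, the largest tolerable SD is

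SD = 20 × √(n/2) / (1.960 + 0.842)

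This is 39.1 mm Hg at 60 per arm, 27.6 at 30 and 22.6 at 20. Losing numbers alone therefore does not undo the statement unless the SD is large or few subjects have a value. Bias is the issue.

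**Simulation in m/s (every input here is an assumption except the sample size).** 65 per arm (section 2.5.1); mean TRV 2.7 m/s; SD 0.5 m/s; correlation of 0 h with 12 h 0.6; true shift -0.30 m/s. A jet is measurable with probability

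P = 1 / (1 + exp(-(TRV - m)/s)), with m = 2.2 or 2.5 and s = 0.15 or 0.3,

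the same rule in both arms. With m = 2.5 and s = 0.15, P is 0.79 at the placebo mean of 2.7 and 0.34 at the iNO mean of 2.4. With m = 2.2 and s = 0.3 the values are 0.84 and 0.66. Across the curves, 63-81% of placebo and 43-64% of iNO subjects have a 12 h value.

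| Analysis | Estimate (true -0.30) | Shrinkage | Power |
|---|---|---|---|
| Raw 12 h difference, available cases | -0.16 to -0.22 | 26-47% | 42-67% |
| Change, 12 h minus 0 h | -0.23 to -0.27 | 12-23% | 52-76% |
| Baseline-adjusted 12 h difference | -0.20 to -0.25 | 17-34% | 55-81% |
| Rank test, no jet placed lowest | not in m/s | n/a | 72-88% |

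Shrinkage is 1 - |estimate|/0.30, taken before rounding; for example 1 - 0.16/0.30 = 47%. With complete data the effect is 0.30/0.5 = 0.6 SD, and 0.6 × √(65/2) - 1.96 = 1.46, which is about 92-93% power.

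**Cross-check in SD units.** Assumed true effect 0.5 SD, 60 per arm; complete-data power is 78%, since 0.5 × √30 - 1.96 = 0.78. Results on available cases:

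- Low values missing by one logistic rule in both arms (30-50% missing on placebo, 40-65% on iNO): raw 0.31-0.42, change 0.42-0.47, baseline-adjusted 0.36-0.45. Power of the raw comparison is 28-53%.
- Values below a fixed cut-off missing (the lowest 20-60% of placebo values): raw 0.25 down to 0.13.
- Missing completely at random, or by a rule that depends only on baseline: 0.50, no bias.
- High values missing in the iNO arm only (22% missing there): 0.69, overstated. With no true effect, the same rule gives a spurious fall of 0.26.

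**Cost of the rank test if its premise is wrong.** In the m/s setting, with jet absence unrelated to pressure, placing no-jet subjects lowest cuts power from 86% to 57% at 20% absent and from 80% to 33% at 30% absent, compared with the available-case test.

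**The case against.** A reader might infer that the effect *is* understated because the largest responders leave the iNO arm. The documents do not support that. They do not link jet loss to low pressure, and they give no missing rate and no reasons for missing echoes. Other patterns give no bias, or bias the other way.

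A reader might also take the 26-47% as the plan's expected loss. It is the figure for the worst-affected estimator. Section 2.4 also lists the change from 0 h, and section 2.5.3 permits adjusted regression; both lose less. With m = 2.2 the baseline-adjusted analysis has about the same power as the rank test (80-81% against 80-88%). The rank test keeps a clear advantage only with m = 2.5.

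A third tempting step is to make the rank comparison the main analysis. That exchanges one untestable assumption for another and is costly if the second is wrong.

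It is also fair to say that an asterisk cannot create a jet, that section 2.5.5 does allow sensitivity analyses, that section 2.5.3 names vasodilation and section 2.5.1 pulmonary artery pressure rather than TRV, and that proof of efficacy rests on the primary outcome.

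What remains is that the echo is unstarred at both times while Aim 3 depends on it, that the reason for a missing TRV is not recorded, and that no not-at-random analysis is specified. An optional analysis chosen later cannot recover a reason that was never captured.

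**Conclusion.** The point holds as a gap in collection and pre-specification: the plan treats its physiologic test as optional data and would analyse it on available cases with no means of checking the assumption. Understatement is a possibility, not a finding. It depends on jets being lost more often at low pressure, and its size depends on the assumed detection curves, SD, correlation and shift. On those assumptions the shrinkage ranges from 12% (change score, mildest case) to 47% (raw 12 h difference, worst case). With random or baseline-only missingness it is zero.

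One limit applies to the less affected estimators. Section 2.2 allows the 0 h echo up to one hour after study drug starts, which could itself dilute a change or baseline-adjusted comparison; the simulations do not include this.

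The primary composite is unaffected. This is a cheap improvement.

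**What to change.** 1. Add the asterisk to the echo, TRV included, at 0 h and 11-12 h.
2. Add one form field for the reason TRV is missing: no jet with an adequate window, inadequate window, not done, or died.
3. Report missing TRV by arm and reason.
4. Name the baseline-adjusted 12 h TRV comparison, already permitted by section 2.5.3, as the main TRV analysis.
5. Pre-specify one not-at-random sensitivity analysis that ranks no jet with an adequate window below every measured velocity, or treats it as left-censored. Keep it as a sensitivity analysis, because it loses power if jet absence is unrelated to pressure.

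The cost is one form field, a few lines of analysis text and a little extra analysis. Both echoes are already scheduled. The sensitivity analysis is only as good as the bedside judgement that the window was adequate, which should be stated when it is reported.
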